6 SAMPLE SIZE DETERMINATION

The sample size for a proof-of-concept study should be large enough to be able to detect a drug effect or surrogate signal, but at the same time expose a minimum number of subjects to an experimental drug combination in a reasonable timeframe within a restricted budget. Sample size was determined based on sample sizes used in similar double-blind, placebo-controlled studies of PTSD and AUD, and based on the estimated recruitment rate over the allotted enrollment timeline. With these factors in mind, we plan to enroll approximately 180 participants to allow screen failures/drop-out prior to randomization of approximately 90 participants across three sites (45 in each treatment arm) within a 24-month enrollment period. We estimate that attrition will be approximately 30%. However, all randomized participants will remain in analysis (intent-to-treat) regardless of how long they participate in the study.

For the primary outcome, we assumed the following success rates based on a similar previous study: Placebo arm 5/45 (11%) or less and 2mg BUP/NLTRX arm 17/45 (38%) or greater. We calculated power for two by two contingency tables for comparison of the treatment and Placebo arm using a Fisher's Exact test with the Walters approximation applying a nominal two-sided alpha level of 0.05. We observe power of 80% or greater for the above assumptions. In addition, a situation with more positive responses in the active treatment arm or fewer positive responses in the placebo arm would increase apparent power.

For secondary outcomes, we estimate that we will have >80% power to detect a medium effect size (Cohen's $f=0.25$, two-sided alpha level of 0.05) at 8 weeks. Under optimal conditions, where the correlation between consecutive observations on the same participant is high, and the variability observed between pairs of time points is fairly constant, fewer participants would be required (see table below). Under a less than ideal, worst-case situation where correlation between measurements is low and the variability observed between pairs of time points changes, the proposed sample size is still large enough to detect a moderate effect size, even after accounting for screen failures and drop-outs.

For the Psychophysiological and Fear Conditioning analyses, a total sample size of 90 (45 per group) will allow for a conservative dataset with over 80% power to detect significant differences between the treatment group against the placebo group at the $\alpha = 0.05$ level. Estimates were based on means and standard deviations from previous study samples.

Estimated Sample Sizes per Group for Detecting a Moderate Effect Size at 80% Power			
Modeling Conditions	AUD Outcome	PTSD Outcome	Higher of PTSD/AUD with Screen Failures and Drop-outs (+15)
High Correlation, Constant Variance	42	30	57
High Correlation, Non-constant Variance	42	63	78
Low Correlation, Constant Variance	81	57	96
Low-Correlation, Non-constant Variance	81	120	135

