7.3.4 FOLLOW-UP VISITS

Assessments occur at screening, baseline, and post-randomization Weeks 1, 2, 4, 6, 8, 10, and 12. There is a visit window of +/- 7 days for follow-up visits.

The investigators and CRCs provide ongoing reinforcement of the patients' commitment to long-term follow-up. The study medication providers emphasize the need to properly adhere to prescribed treatments or to call to revise the treatments if side effects occur or therapeutic effects are lost.

Adherence to SL-BUP medication is confirmed by pill count. Concomitant medications are updated at each of these visits.

If participants experience side effects that cannot be managed by adjustments in the timing of the medication (i.e., taking at bedtime, etc.), they may have their medication titration either held or the medication dosing may be decreased (i.e., less frequent).

The CRC makes a telephone (t) contact with the participant between face-to-face visits to remind the participant of the next office visit and to check on adherence to the study medication and if there have been any serious adverse events.

*Psychophysiological assessments are optional to not be a barrier to enrollment or randomization.

The one-day psychophysiological assessment is repeated at Week 2.

The two-day psychophysiological assessment is repeated at Week 8.

At Week 8, the participant remains on the assigned treatment and dose from Week 8 to Week 12.

While every attempt is made to retain the participant in the study on medication for the full 12 weeks, the participant may discontinue medication at any point and remain in the study for assessments through Week 12.

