7.3.6 EARLY TERMINATION VISIT

If a participant exits prior to Week 8, all procedures for Week 8 are completed. If the participant exits after Week 8 but prior to Week 12, all Week-12 procedures are completed.

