10.5 SAMPLE SIZE

The sample size for a proof-of-concept study should be large enough to be able to detect a drug effect or surrogate signal, but at the same time expose a minimum number of participants to an experimental drug combination in a reasonable timeframe within a restricted budget. Sample size was determined based on sample sizes used in similar double-mask, placebo-controlled studies of AUD and PTSD, and based on the estimated recruitment rate over the allotted enrollment timeline.

With these factors in mind, we plan to enroll approximately 180 participants to allow for screen failures/dropouts prior to randomization.

With respect to sample size, the goal is to obtain at least 90 participants randomized to either of the two retained arms (XRNTX/2mg BUP arm and PLACEBO arm). Recruitment will occur over a 24-month enrollment period. If this goal is met with time left in the enrollment period, sites will be allowed to randomize additional participants but will not exceed the original planned sample size of 135 randomized participants across all 3 originally planned study arms.

To ensure balance within each treatment group we will use stratified randomization on site, presence/absence of concomitant antidepressants, and gender. We plan to use blocking within each stratum of the randomization scheme to balance treatment assignments. We estimate that attrition will be approximately 30%. However, all randomized participants will remain in analysis (intent-to-treat) regardless of how long they participate in the study.

For the primary outcome, we assume 90 randomized participants (allowing for screen failures/dropouts) allotted equally among the two study arms and with the success rates shown in the below table. We calculated power for two by two contingency tables for comparisons with each treatment arm and the Placebo arm using a Fisher's Exact test with the Walters approximation applying a nominal two-sided alpha level of 0.05.

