In examining our primary outcome, we provide a table of power calculations with a range of potential placebo and treatment responses for a sample size of 45 in each group. The value in orange (0.560) is from the original protocol where the assumption was for an 11% (5/45) positive response rate in the placebo arm and a 31% (14/45) positive response rate in the active treatment arm. All cells shaded in yellow have a value of 0.7 or greater and all cells shaded in green have a value of 0.8 or greater. A sample size of 45 in each group will be able to detect a clinically meaningful difference between groups. For example, a treatment response of ≥38% (17/45) in the active treatment arm (consistent with ALKS-4561 for depression) and ≤11% (5/45) in placebo arm (conceivable in a dual-diagnosed PTSD-alcohol population) would have power of 0.8 or greater. In addition, a situation with more positive responses in the active treatment arm or fewer positive responses in the placebo arm would increase apparent power.

		Treatment Positives									
		24%	27%	29%	31%	33%	36%	38%	40%	42%	44%
Placebo Positives	11	11	12	13	14	15	16	17	18	19	20
		0.860	0.908	0.941	0.964	0.979	0.988	0.993	0.996	0.998	0.999

4%	2	0.714	0.791	0.853	0.900	0.934	0.958	0.975	0.985	0.991	0.995
7%	3	0.556	0.651	0.734	0.804	0.861	0.905	0.937	0.960	0.975	0.985
9%	4	0.409	0.506	0.600	0.687	0.762	0.826	0.877	0.916	0.944	0.964
11%	5	0.286	0.375	0.467	0.560	0.647	0.726	0.795	0.851	0.895	0.929
13%	6	0.192	0.265	0.348	0.437	0.527	0.615	0.696	0.767	0.828	0.877
16%	7	0.125	0.180	0.248	0.326	0.412	0.500	0.587	0.669	0.743	0.807
18%	8	0.081	0.119	0.170	0.235	0.309	0.392	0.478	0.565	0.647	0.723
20%	9	0.057	0.079	0.114	0.163	0.224	0.295	0.375	0.460	0.545	0.628

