7.3 Handling of Dropouts and Missing Data

Analysis of the primary and exploratory outcomes will be based on a mixed-effect model of repeated measures (MMRM) using data from all time points to account for missing data and thereby maximize information used for the analyses. These models treat missing data as ignorable missing, assuming any missing data are missing at random. No imputation processes will be used to replace missing data. However, every effort will be made to minimize missing data.

Additionally, because missing observations have the potential to alter the results of analyses, we will examine whether the pattern of missing data is different among the groups. If there are no systematic differences between those with and without missing data, the data will be considered to be missing at random. If there are significant differences in dropout or missing data patterns between treatment arms, we will conduct sensitivity analyses to determine the impact of missing information on the treatment comparisons.

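### The stated 80% primary power assumes no missing Week 8 data despite 30% expected attrition, and the worst-case claim for the continuous outcomes fails against its own table

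*SAP*

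**What the plan says.** **Primary outcome.** SAP 6 assumes response in at most 5/45 (11%) on placebo and at least 17/45 (38%) on active treatment, tested by Fisher's exact test with the Walters approximation at two-sided 0.05. It concludes: "We observe power of 80% or greater for the above assumptions". Protocol 10.5 describes the 11% placebo rate as "conceivable in a dual-diagnosed PTSD-alcohol population) would have power of 0.8 or greater", and its power table prints 0.795 for that cell.

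**Losses.** Protocol 10.5 states "We estimate that attrition will be approximately 30" percent, and SAP 6 repeats it. Both add only that everyone randomized stays in the intention-to-treat analysis. The 180 to be enrolled are "to allow screen failures/drop-out prior to randomization of approximately 90 participants". SAP 7.3 says "No imputation processes will be used to replace missing data".

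**Size.** The protocol treats 90 as a minimum. If it is reached early, "sites will be allowed to randomize additional participants but will not exceed the original planned sample size of 135 randomized participants", counted across the three original arms.

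**Continuous outcomes.** Both sections claim more than 80% power for Cohen's f = 0.25. They say the sample suffices even with low correlation, changing variance and drop-outs. The table beside this claim is headed as sizes per group. In its worst row it asks for 81 (AUD) and 120 (PTSD), or 135 after adding 15 for losses.

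**Psychophysiology.** Both sections claim over 80% power with all 90 participants. Protocol 4.1 makes these tests optional, and SAP 3.1 moves the startle analysis to a supplemental SAP.

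**The concern.** Membership of the intention-to-treat set does not supply a missing Week 8 response. A participant without one contributes to the Week 8 contrast only through what the mixed model borrows from other visits. Power computed on 45 per arm is therefore the figure for complete Week 8 data, yet it stands beside a 30% attrition estimate without qualification.

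The worst-case sentence is a plainer problem, because the table next to it asks for more participants than the trial has.

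What is at stake is planning. SAP 7.7 already treats a non-significant result as inconclusive, so a null finding would not be over-read. But 90 is a floor and sites may go beyond it. Anyone deciding whether to stop at 90 is shown 80% power with nothing deducted for attrition.

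**Working it through.** **Primary: reproducing the plan.** Inputs are p1 = 5/45, p2 = 17/45, n = 45 per arm and two-sided alpha 0.05 (SAP 6). The Walters approximation is

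power = Φ{ √(2n) · [arcsin √(p2 − 1/(2n)) − arcsin √(p1 + 1/(2n))] − 1.960 }.

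At n = 45: √90 × (0.6504 − 0.3571) = 2.782, and Φ(2.782 − 1.960) = 0.795. This matches the protocol's table; exact Fisher also gives 0.795, and the rounded rates 0.11 and 0.38 give 0.805. So the stated figure is right to rounding for 45 evaluable per arm. Strictly, 46 are needed for 0.80.

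**Primary: with Week 8 data missing.** Same formula, n = 45 × (1 − share missing):

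| Missing Week 8 | n per arm | Power |
|---|---|---|
| 0% | 45 | 0.795 |
| 10% | 40.5 | 0.74 |
| 15% | 38.25 | 0.71 |
| 20% | 36 | 0.68 |
| 30% | 31.5 | 0.61 (31: 0.60; 32: 0.62) |

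Exact Fisher at 31 and 32 per arm gives 0.61 and 0.63. If the 30% are instead counted as failures, the rates become 0.7 × 11.1% = 7.8% and 0.7 × 37.8% = 26.4% with n = 45, and power is 0.57.

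**Possible recovery from Week 4.** Suppose all 30% lack Week 8 data but all have Week 4 data. As an approximation borrowed from linear models, n_eff = 1/[(1 − r²)/31.5 + r²/45], with r an assumed Week 4 to Week 8 correlation. For r = 0.5, n_eff = 34.1 and power is 0.65. For r = 0.7, n_eff = 36.9 and power is 0.69.

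**Size for 80%.** 46/0.7 = 65.7, so 66 per arm or 132 randomized, if all 30% lack Week 8 data.

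**Table: reproducing it.** Use a repeated-measures group-by-time F test with k groups, m visits, correlation ρ, sphericity ε and *total* N: λ = f²·N·m·ε/(1 − ρ), df1 = (k − 1)(m − 1)ε, df2 = (N − k)(m − 1)ε, f = 0.25. The documents do not state m, ρ or ε. With the values below and k = 3, all six distinct entries come out exactly, as totals. The k = 2 columns use the same settings.

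| Outcome (m, ρ, ε) | Printed | k = 3 total | k = 2 total | k = 2 ÷ 0.7 | Power, N = 90 | Power, N = 63 |
|---|---|---|---|---|---|---|
| AUD (2, 0.5, 1) | 42 | 42 | 34 | 49 | 0.997 | 0.974 |
| AUD (2, 0, 1) | 81 | 81 | 66 | 95 | 0.913 | 0.789 |
| PTSD (4, 0.5, 1) | 30 | 30 | 24 | 35 | 1.000 | 0.999 |
| PTSD (4, 0.5, 1/3) | 63 | 63 | 50 | 72 | 0.969 | 0.890 |
| PTSD (4, 0, 1) | 57 | 57 | 46 | 66 | 0.986 | 0.925 |
| PTSD (4, 0, 1/3) | 120 | 120 | 98 | 140 | 0.773 | 0.616 |

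N = 63 is 90 × 0.7. The worst row with its allowance, 120 + 15 = 135, equals the original three-arm total in Protocol 10.5.

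**Worst-case sentence on each reading.** As printed: 135 needed per group against 45. As a three-arm total: 135 against 90. Redone for two arms: 98 before any loss, and 140 at 30% attrition, against 90. It fails each time, and the first two readings need no inferred settings.

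**Psychophysiology.** The means and standard deviations behind this claim are not given, so it cannot be recomputed. The check is textual: it counts all 90 for tests that participants may decline.

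**The case against.** - *The statement is conditional and correct for 45 per arm, and a proof-of-concept trial may choose its size on feasibility.* True, and both sections say feasibility drove the choice. Low power can be accepted, but the figure should reflect the losses expected in the same paragraph.
- *The 30% is never defined as missing Week 8.* This stands. Under Protocol 7.3.6, "If a participant exits prior to Week 8, all procedures for Week 8 are completed", and under 7.3.4 "the participant may discontinue medication at any point and remain in the study for assessments through Week 12". It is why the result is a range with 0.6 at its lower end. The documents do not say how much these provisions recover, and the power statement does not rely on them.
- *The planned test is a logistic mixed model, and Walters is conservative.* An unadjusted Week 8 logistic Wald test has power 0.849 at 45 per arm, 0.799 at 40, and 0.65 to 0.68 at 31 to 32. On that scale about 10% missing still leaves roughly 80%, and 41 evaluable per arm suffice (41/0.7 = 58.6, so 59 per arm, 118 randomized). This softens the loss, but 30% missing remains well below 80%, and it is not the method behind the stated figure.
- *The protocol shows a wide power grid and permits more than 90.* The grid varies response rates, not attrition. The option to enlarge is the reason the figure matters.
- *The table settings are inferred, and two visits for AUD sits oddly with frequent drinking assessments.* Fair. The two-arm powers depend on those settings; the failure of the sentence does not.
- *SAP v4.0 raised the CAPS-5 threshold from 8 to 10 points, while 5/45 and 17/45 also stand in the protocol under the 8-point rule.* This also stands. Restated power should say which definition the rates were set for.

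**Conclusion.** The point holds. The 80% is right to rounding only if all 90 have Week 8 data. By the plan's own method, power falls to about 0.74, 0.68 and 0.61 with 10%, 20% and 30% missing, and to 0.57 with drop-outs counted as failures. Where the trial lies in that range depends on how many of the 30% lack Week 8 data, which neither document states.

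The worst-case sentence is wrong on every reading of the table. That the table was mislabelled and carried over from three arms is probable rather than certain, because the settings that reproduce it are inferred. The practical shortfall is smaller than the printed 135 against 45 suggests. For two arms, five of the six distinct cells have power of at least 0.91 at 90, and four stay at 0.89 or more with 63 completers. Only low-correlation AUD (0.789) and worst-case PTSD (0.616) fall below 80%.

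The psychophysiology claim is leftover text in SAP 6 and unsupported for the optional subset in the protocol. All of this should be corrected; none of it invalidates the planned analysis.

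**What to change.** In Protocol 10.5 and SAP 6:

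1. State primary power as a range, from 0.795 with complete Week 8 data to about 0.6 if 30% lack it. Say how many are expected to lack it, and for which CAPS-5 threshold the response rates were set.
2. Correct the per-group label. Recompute the table for two arms, replace the flat addition of 15 with n/(1 − 0.30), and state the visits, correlation and sphericity assumed.
3. Delete the worst-case sentence and say which conditions keep 80% power.
4. Remove the psychophysiology power claim from SAP 6. In the protocol, restate it for the number expected to take the optional tests.

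The cost is editing, and a less favourable stated power. It requires no additional participants and changes no analysis or decision rule. Whether to use the existing room above 90 remains the study team's choice, made with the right figure in view.

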7 STATISTICAL / ANALYTICAL ISSUES

7.1 General Rules

All statistical computations will be performed and data summaries will be created using SAS 9.4 or higher. If additional statistical packages are required, these will be discussed in the study report. For summaries of study data, categorical measures will be summarized in tables listing the frequency and the percentage of participants; continuous data will be summarized by presenting mean, standard deviation, median and range; and ordinal data will be summarized by only presenting median and range. Model-based analyses described in Section 9 will be used to obtain point estimates and associated confidence intervals for various measures as well as p-values for comparisons of data between treatment groups. Note: initial models will include the high dose treatment arm; however, if the model cannot converge due to the small number of participants randomized to this arm prior to removal from the study, then the model will only compare outcomes between the low dose and placebo treatments. P-values presented will be based on two-sided tests unless otherwise specified and generally only adjusted for randomization factors (study site, gender, and presence of concomitant antidepressants). Note: in the event a model cannot converge due to small sample sizes for a specific randomization factor, it will be removed from the model. For continuous outcomes, checks of normality will be performed and if required, transformations or non-parametric tests will be employed.

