10.4.2 ANALYSIS OF THE PRIMARY EFFICACY ENDPOINT(S)

The primary dependent variable will be response status at Week 8 for each participant. A positive response is defined as a decrease from baseline of at least 8 points on the CAPS-5 score and a reduction of at least 1 risk level of alcohol use, as defined by WHO, at Week 8. Response data will be analyzed using mixed logistic regression with treatment group, measurement visit as a categorical variable, gender, site, presence/absence of anti-depressants, and other potential confounders as explanatory variables. A treatment group by measurement visit interaction will be included to account for the longitudinal nature of the data with the Week 8 effect being the primary outcome of interest. A two-sided p-value will be reported from the primary analysis for the all pairwise comparisons of SL-BUP/XR-NTX treatment and placebo groups.

As a complement to the primary outcome, the AUD and PTSD components of the composite will be evaluated individually. Difference in heavy alcohol use at Week 8 (defined as *>4 standard drinks/sessions for men and >3 standard drinks/sessions for women*) will be analyzed using a generalized-linear mixed model with treatment group, gender, site, presence/absence of anti-depressants, and other potential confounders as explanatory variables. Difference in reduction of PTSD symptoms at Week 8 (as measured by the CAPS-5) will be analyzed using a generalized-linear mixed model with treatment group, gender, site, presence/absence of anti-depressants, and other potential confounders as explanatory variables. For both outcomes, a treatment group by visit interaction term will be included to account for the longitudinal nature of the data, with Week 8 effect being the primary outcome of interest.

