5 ANALYSIS POPULATIONS

5.1 Intention-to-Treat

The primary and exploratory analyses will be based on the intention-to-treat (ITT) principle, with data from all participants analyzed according to the arm to which they were randomized irrespective of the amount intervention received. This includes participants initially randomized to the high-dose treatment arm (SL-BUP 8mg and XR-NTX 380mg) that was removed from the protocol (Version 5). Participants who receive intervention but do not complete the study will be used in all analyses for which data are available. This approach ignores noncompliance, protocol deviations, withdrawal and lost-to-follow-ups. Analysis of the ITT population avoids overoptimistic estimates of the efficacy of an intervention resulting from the removal of non-compliers, accepting that protocol deviations occur in actual clinical practice (Heritier, Gebski, & Keech, 2003).

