7.7 Multiple Comparisons and Multiplicity

One single primary formal hypothesis test is planned for this study at the 0.05 level of significance, which is the comparison of the SL-BUP + XR-NTX treatment group vs. placebo for the primary outcome at the primary timepoint (Week 8). Additionally, regardless of significance of the primary outcome, statistical significance of the secondary outcomes will be assessed, with adjustment for multiple comparisons using the Benjamini-Hochberg false discovery rate correction to maintain the nominal alpha level of 0.05 (Benjamini & Hochberg, 1995). Primary and secondary hypothesis tests resulting in nonsignificant p-values will be interpreted as inconclusive. All other treatment group comparisons will be considered descriptive in nature with no adjustment for multiple comparisons, and all confidence intervals will be generated using 95% bounds.

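### SAP 7.1 lets model convergence decide whether the discontinued 8 mg arm is in the primary model; the arm set should be fixed in advance (low severity)

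*SAP*

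**What the plan says.** SAP 7.1 opens the rule broadly: "Model-based analyses described in Section 9 will be used to obtain point estimates and associated confidence intervals". The primary model in SAP 9.3 is therefore covered. It then says that "initial models will include the high dose treatment arm; however, if the model cannot converge due to the small number of participants" randomized to that arm before its removal, "then the model will only compare outcomes between the low dose and placebo treatments". A second rule in the same section drops a stratification factor: "in the event a model cannot converge due to small sample sizes for a specific randomization factor, it will be removed from the model".

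SAP 5.1 attaches no condition to the analysis population: "This includes participants initially randomized to the high-dose treatment arm (SL-BUP 8mg and XR-NTX 380mg) that was removed from the protocol" at version 5.

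SAP 7.7 plans one formal test at 0.05, the "comparison of the SL-BUP + XR-NTX treatment group vs. placebo for the primary outcome" at Week 8, and gives no dose. Protocol 10.4.2 promises a two-sided p-value "for the all pairwise comparisons of SL-BUP/XR-NTX treatment and placebo groups".

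Protocol 10.2 describes two groups, and protocol 10.5 sets its recruitment goal for the two retained arms. SAP 6 computes power for 2 mg versus placebo only. SAP 9.3 and its code do not say how many levels the treatment variable has.

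**The concern.** The trial has one confirmatory comparison. The set of participants in its model ought to be known before anyone sees outcomes by arm. Under SAP 7.1 it is not, because whether a small third arm stays in is settled by a fitting message. In a logistic mixed model with treatment-by-visit terms, that message can depend on how the few 8 mg participants responded as well as on how many there are. SAP 4.4.2 holds the treatment codes until after database lock, so the choice falls after unmasking.

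The SAP does not define non-convergence, list estimation steps to try first, or say whether the arm or a stratification factor is dropped first. At stake are the reproducibility of the primary estimate and a clear statement of who was analysed and which dose was tested.

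**Working it through.** **1. The plan's own power figure.** Inputs from SAP 6 and protocol 10.5: 5/45 on placebo, 17/45 on 2 mg, 45 per arm, two-sided 0.05, Fisher's exact test with the Walters approximation. The approximation moves each rate 1/(2n) toward the other.

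- Adjusted rates: 5.5/45 = 0.1222 and 16.5/45 = 0.3667.
- d = 2 × (arcsin √0.3667 − arcsin √0.1222) = 2 × (0.6504 − 0.3571) = 0.5866.
- Power = Φ(d × √(45/2) − 1.960) = Φ(0.5866 × 4.743 − 1.960) = Φ(0.822) = 0.795.

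This equals the protocol's table cell (0.795), which SAP 6 gives as 80% or greater. Exact enumeration of Fisher's test also gives 0.795. Only two arms enter the calculation, so a two-arm primary model leaves it unchanged.

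**2. Who is in the primary model.**

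| Place | 8 mg participants |
|---|---|
| SAP 5.1 | In, without condition |
| SAP 7.1 | In, unless the model fails to converge |
| SAP 7.7 | Not settled; no dose named |
| SAP 9.3 | Not settled; number of treatment levels not given |
| SAP 6, protocol 10.2 and 10.5 | Not part of the comparison; two arms only |

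**3. Can the trigger depend on responses?** SAP 9.3 analyses Weeks 4, 8 and 12. A third arm adds one treatment term and two treatment-by-visit terms, 1 + (3 − 1) = 3 parameters, estimated from that arm alone. If all its outcomes at a visit are the same, the term for that visit has no finite maximum-likelihood estimate. The chance of this at one visit is p^n + (1 − p)^n. The arm size n is not in the documents, so a range is assumed. The rates of 11% and 31% come from the protocol's original power assumption.

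| Assumed n | p = 11% | p = 31% |
|---|---|---|
| 3 | 0.71 | 0.36 |
| 5 | 0.56 | 0.16 |
| 10 | 0.31 | 0.02 |
| 15 | 0.17 | 0.004 |

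For example, with n = 5 and p = 31%: 0.31^5 + 0.69^5 = 0.003 + 0.156 = 0.159. At a fixed arm size the rule could therefore lead to either model, depending on the responses. These are probabilities of uniform outcomes, not of non-convergence. Software may report convergence with an extreme estimate, and models fail for other reasons too.

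**4. How far does the tested contrast move?** With its own treatment and treatment-by-visit terms, the 8 mg arm reaches 2 mg versus placebo only through the shared covariate effects and the random-intercept variance. Two simulations fitted the model with and without that arm. Both assumed 45 per retained arm, a random-intercept SD of 1.5 and about 30% attrition. Both used quadrature maximum likelihood, not the GLIMMIX default.

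- *Datasets with mixed outcomes in every arm at every visit.* Assumptions: 5, 10 or 15 participants on 8 mg; response 11% on placebo, 31% or 38% on 2 mg, 31% on 8 mg; 300 datasets per setting before selection. The 5% verdict at Week 8 differed in 1.3% to 3.9%. The median absolute change in the log odds ratio was 0.05 to 0.08, against a standard error near 0.9. Isolated unstable fits moved much more: the SD of the change reached 0.90 in one setting.
- *Datasets where all observed 8 mg outcomes at Week 8 were identical.* Assumptions: 3 or 5 participants on 8 mg; response 11% on placebo, 30% on 2 mg, 11% or 30% on 8 mg; about 245 datasets per setting. The verdict differed in 0% to 1.2%. The median absolute change was 0.002 to 0.016.

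**The case against.** The best defence is that SAP 7.1 is written in advance and runs one way: fit with the arm, and drop it only if the fit fails because the arm is small. A reader might infer that the primary analysis is selected on its results. The text does not support that, because the trigger is a fitting failure and not the size, direction or significance of the 2 mg effect.

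A reader might also infer from SAP 7.7 that the two doses could be pooled. The label fits both, but nothing proposes pooling. SAP 7.1 separates high dose from low dose, SAP 4.1 and 4.3 define Treatment A as 2 mg, and SAP 6 powers that arm.

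A third inference is that keeping the arm would create three confirmatory contrasts. SAP 7.7 allows one primary test and treats comparisons beyond the primary and secondary tests as descriptive. Under the current two-group protocol, the pairwise wording in 10.4.2 amounts to one comparison.

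Finally, keeping every randomized participant in the model, with 8 mg as its own level, is a coherent reading of ITT. All four points stand and limit the severity. They do not reconcile SAP 5.1 with 7.1, supply a convergence criterion or name the dose.

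**Conclusion.** The point holds at low severity. The arm set of the primary model is conditional on an event that can depend on 8 mg responses and is seen only after unmasking, and the sections disagree about who is analysed. The likely consequence for 2 mg versus placebo is small: about 0% to 4% of 5% verdicts changed in simulation. That range rests on assumed 8 mg arm sizes of 3 to 15, the assumed response rates, random-effect SD and attrition, and an estimation method other than the planned software's default. The uniform-outcome probabilities show only that the trigger can depend on responses. They should not be quoted as the chance that the model changes.

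**What to change.** - **SAP 5.1, 7.1 and 9.3:** define the primary model as all participants randomized to the two retained arms (2 mg and placebo), analysed as randomized. State that the treatment variable has two levels.
- **SAP 7.1:** delete the convergence condition for the 8 mg arm.
- **SAP 7.7:** name 2 mg versus placebo at Week 8 as the single test.
- **8 mg participants:** describe them separately, and add one pre-specified sensitivity model that includes them as their own level.
- **Protocol 10.4.2:** align the pairwise wording with the single comparison.

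Protocol 10.1 has the SAP finalized before lock and unmasking, so these edits belong before then. The cost is wording, plus slightly less information on visit and covariate effects. Planned power stays at 0.795.
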